8. ADVERSE EVENTS

8.1 Expected Adverse Events

In known studies where LISW was used for treatment of ED, there have been no reported adverse events (Ref. 2, Ref. 3). However minimal side effects like Transitory reddening of the skin, pain small bruising and swelling can be expected.

8.2 Serious Adverse Events

Serious injury or death

Any adverse event (penile hematoma or penile fracture) and eventual complication must be recorded at any time during the treatments and the follow up visits, and throughout the entire study duration. Patients will be instructed to alert the study investigator by telephone of any side effects occurring in the period after the treatment and until the study end.

For Reporting of adverse events see section 9

9. DATA AND SAFETY MONITORING PLAN

The study investigators will report to a surgeon monitor [name] in the department of urology (who is not involved in the study) to ensure data quality and subject safety. The investigators will conduct continuous reviews of the data and subject safety, keeping track of the number of subjects, significant toxicities in accordance with the protocol and observed responses, which will be discussed at research committee meetings. All grade 3-5 adverse events (CTCAE v4.0), regardless of association with the LISW, will be entered into study database and reviewed at research committee meetings. In addition, all adverse reactions considered “serious” will be entered into research database and reviewed by the Surgeon monitor on an ongoing basis. If a death occurs within 30 days of LISW treatment and is determined to be related to the study, the investigators will notify the Department Chair [name] within 1 business day. If an increase in the frequency of grade 3 or 4 adverse events is noted in the study, a report will be submitted to the Department Chair [name] at the time the increased rate is identified. If at any time the principal investigator stops enrollment or stops the study due to safety issues, the Department Chair ([name]) will be notified within 1 business day and a formal letter will be sent to the Department Chair ([name]) to be received within 10 business days.

10. STATISTICAL CONSIDERATIONS

10.1 Primary Study Endpoints

The IIEF-EF questionnaire (appendix I) was chosen as the primary clinical efficacy assessment tool in this study. The total score (range 0-30) will be used for statistical analysis.

10.2 Secondary Endpoints

Sexual activity improvement leading to optimal penetration at follow-ups will be done according to:

SEP 2 & 3 at follow-ups
GAQ at follow-ups
EHS at follow-ups.

Endpoint Measurements: using CRF/questionnaire analysis

10.3 Endpoint definitions

IIEF-EF Questionnaire see appendix I
SEP 2 & 3 Questionnaire see appendix II
GAQ Questionnaire see appendix III
EHS Questionnaire see appendix IV

10.4 Sample size, accrual and study duration

TOTAL SAMPLE SIZE: 80
TOTAL ACCRUAL: 80
ACCURAL DURATION: 12 MONTHS
STUDY DURATION: 7 months

10.5 Statistical Analysis and Power calculation

The average and standard deviation of all relevant variables, including demographic and baseline characteristics, primary and secondary outcomes will be calculated.

IIEF-EF and EHS scores will be analyzed using ANOVA with repeated measures throughout the study, in order to compare the trends of groups A and B.

GAQ, SEP and success rates will be analyzed and compared between the groups according to Fisher's exact test in each of the endpoints. The statistical significance will be set at $P < 0.05$.

Demographic characteristics such as age and ED duration will be compared between groups A and B using student's test. Other demographic characteristics, such as medical background and risk factors will be compared between these groups using Fisher's exact test.

A sample of 80 men with failing scores on the IIEF SEP2 question will be randomized 1:1 into one of two arms (low intensity or high intensity treatment) using a permuted random block algorithm. We hypothesize that following placebo treatment between 0 and 5% of men will pass the SEP2 question and at least 35% of men treated at either intensity level will pass. We have two co-primary

endpoints, the percentage of men passing after low intensity and high intensity relative to placebo, which will be assessed by two independent Fisher’s exact tests. Each of these tests will be conducted with a 0.025 alpha error level to allow for a 0.05 experiment wide type I error rate. Power calculations done in SAS 9.4 suggest that with 40 men randomized into each group we will have at least 85% power to detect the difference between a 5% and 35% response rate. So long as our non-compliance/drop-out rate remains above 10% will will have at least 80% power (see Figure 1).

Computed N per Group			
Index	Nominal Power	Actual Power	N per Group
1	0.80	0.813	37
2	0.85	0.852	40
3	0.90	0.900	45

Figure 1. Sample size needed for 80% 85% and 90% nominal power for a Fisher’s exact test with alpha = 0.025 (using an exact conditional distribution with the Walters normal approximation method).

10.6 Randomization:

80 patients will be randomized 1:1 to treatment groups with 40 patients each. An online based randomization tool called randomized.org will be used. This will be prepared beforehand, with treatment option printed on the paper and then sealed in an envelope (80 envelopes). Each would have Patients ID number printed out side and randomization information inside. This would be opened after a patient has signed the informed consent and is ready to receive treatment. The PI nor the study coordinator will not have the knowledge of patient’s treatment group beforehand.

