1.4 Preliminary Studies

Contemporary literature shows two important studies in this field both conducted by Vardi et al^{7,8}.

The efficacy trial study published in 2010 recruited 20 men with vasculogenic ED and were given serial 2 sessions of treatment for about 3 weeks followed by 3 – week no intervention period. At 1-month duration there was a significant improvement in their erectile function measured by International Index of Erectile Function ED (IIEF-ED) domain scores (20.9 5.8 vs 13.5 4.1, $p < 0.001$). This significant result was consistent at 6-month follow up. Moreover, no pain or adverse event was noted during the follow-up period.

The second randomized, double-blind, sham controlled study by showed that treatment group showed better outcome than control group measured using International Index of Erectile Function-Erectile Function domain (mean SEM 6.7 0.9 vs 3.0 1.4, $p 0.0322$) at the first follow-up. Additionally, penile hemodynamics improve significantly in the treatment group in comparison to control group (maximal post-ischemic penile blood flow 8.2 vs 0.1 ml per minute per dl, $p 0.0001$).

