2. HYPOTHESIS

2.1 Alternate Hypothesis (H_A):

Active Treatment groups will show a >2-point increase in the IIEF-EF score from baseline for mild erectile dysfunction, and >5 points for moderate erectile dysfunction and will show significant change.

2.2 Null Hypothesis (H₀):

There is no difference from baseline and after-treatment in Treatment groups for alleviating ED measured using IIEF-EF score.

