3. OBJECTIVES

3.1 Primary Efficacy Objective

To evaluate change of IIEF-EF score⁹ from baseline to follow-ups 1, 3 and 6 months' post treatment (appendix I).

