5.3 Cancellation Guidelines

The following are reasons for withdrawal of subjects from the study:

- A subject does not meet the eligibility criteria; (the subject will be considered a screen failure).
- A subject withdraws consent,
- A subject die's during protocol participation from causes other than the study treatment (not due to adverse events) or
- A study investigator decides the subject should be withdrawn from the study (e.g. subject non-compliance)

Regardless of reason for withdrawal, once a patient has been randomized to an arm, an intention to treat analysis will be performed.

All subjects who either screen fails, is withdrawn from the study or has completed all visits should be de-enrolled from the research database within 48 hours.

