7.3 Pre-Treatment Procedures and Evaluations

Upon evaluating the inclusion/exclusion criteria, patients will be recruited to the study and randomized into one of the two groups in a 1:1 ratio (randomization will be performed by a computer software maintained by the Department of Urology). Patients randomized to the treatment groups will be instructed to stop any use of PDE5i for 4 weeks prior to first treatment session and refrain from using any other ED therapy option during the study. They will be instructed to undergo a PDE5i washout period of 4 weeks prior to treatment and to avoid using PDE5i or any other ED treatment during the entire study duration (shockwave treatment and follow-ups). After the washout period and before the first treatment session, patients will answer the IIEF-EF, SEP and EHS questionnaires for baseline evaluation.

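### The IIEF-EF is to be analysed by repeated-measures ANOVA with no baseline covariate, fitting method or rule for missed visits, which does not fit the intention-to-treat promise; a baseline-adjusted mixed model would fit it better

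*Combined protocol and SAP*

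**What the plan says.** Section 10.1 makes the IIEF-EF total score the primary efficacy measure. Its analysis in 10.5 is one sentence: "IIEF-EF and EHS scores will be analyzed using ANOVA with repeated measures throughout the study", with the aim of comparing the trends of groups A and B. No covariate, estimation method, covariance structure, missed-visit rule or sensitivity analysis is given there or elsewhere. Drop-out is mentioned only in the power sentence for SEP2.

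Other sections bear on this:

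- **5.3** promises that, whatever the reason for withdrawal, "once a patient has been randomized to an arm, an intention to treat analysis will be performed".
- **2.2** states the null hypothesis within the treatment groups ("There is no difference from baseline and after-treatment in Treatment groups"), and **3.1** sets the objective as change "from baseline to follow-ups 1, 3 and 6 months". The analysis therefore has to give within-arm change as well as A v B.
- **7.3** places the baseline after the washout: "before the first treatment session, patients will answer the IIEF-EF, SEP and EHS questionnaires for baseline evaluation". The study calendar (Section 17) appears to mark the questionnaires at screening and at the three follow-ups, but not at Visit 2. The table may have been damaged in extraction.
- **7.3** describes randomisation before the 4-week washout. **10.6** suggests a later point for opening the envelope: "This would be opened after a patient has signed the informed consent and is ready to receive treatment".

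**The concern.** Each man should have four IIEF-EF scores: baseline and months 1, 3 and 6. The classical procedure needs all four, so one missed visit removes all of a man's scores, and the men analysed are then not the men randomised. Three things are at stake.

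- Power falls even when visits are missed at random.
- If poor responders leave, completers overstate the within-arm change of 2.2 and 3.1, even when equal numbers leave each arm.
- If poor responders leave one arm more than the other, A v B is biased too.

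If randomisation precedes the washout, as 7.3 describes, some randomised men may not even have a post-washout score. The plan has no rule for them.

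**Working it through.** **The plan's own figure.** There is none for the IIEF-EF. The only power figure in 10.5 is for SEP2. The Walters formula, two-sided alpha 0.025, 40 per group, 5% v 35%, gives Φ(2√(80×0.25) × |arcsin√0.0625 − arcsin√0.3375| − 2.241) = Φ(8.944 × 0.367 − 2.241) = 0.852. This matches the plan's table but says nothing about the IIEF-EF.

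**Inputs.** From the pilot in 1.4, "20.9 5.8 vs 13.5 4.1", I read a baseline SD of 4.1 and a follow-up SD of 5.8. Reading these as SDs is an assumption. From 10.6: 40 men per arm. Also assumed: correlation r = 0.5 between baseline and follow-up, 0.7 between follow-ups, a constant 3-point A-B difference, two-sided 0.05, and all missingness rates.

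**1. Men kept.** With each follow-up visit missed independently, complete cases number 80 × 0.95³ = 68.6 at 5% and 80 × 0.90³ = 58.3 at 10%. Men with at least one follow-up score number 80 × (1 − 0.10³) = 79.9 at 10%.

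**2. Power, same averaged contrast on both sides.**
- Variance of the three-visit mean: 5.8² × (1 + 2×0.7)/3 = 26.91. Covariance with baseline: 0.5 × 5.8 × 4.1 = 11.89.
- Change from baseline: 26.91 + 16.81 − 2×11.89 = 19.94, SD 4.47. SE = 4.47 × √(2/40) = 1.00; noncentral-t power 0.84.
- Baseline-adjusted: 26.91 − 11.89²/16.81 = 18.50, SD 4.30. SE = 0.96; power 0.87.
- The same arithmetic gives 0.68 v 0.77 at r = 0.3 and 0.98 v 0.98 at r = 0.7, so the gain from the covariate is 0 to 9 points.
- With 10% of visits missed (29.2 complete cases per arm): SE = 4.47 × √(2/29.2) = 1.17; power 0.71. The mixed model has 0.85 by simulation.

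**3. Power, test across visits** (simulated: ANOVA group-by-time v the model's joint 3-df test of the A-B differences). With 10% missed: 0.63 v 0.70. On full data the model's test is weaker: 0.78 v 0.72.

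**4. Bias when the least improved men leave.** Suppose loss follows the month-1 change, whose variance is 33.64 + 16.81 − 2×11.89 = 26.67 (SD 5.16). Its covariance with the averaged change is 26.91 − 11.89 − 11.89 + 16.81 = 19.94. Losing the lowest fraction q shifts the completers' mean averaged change by (19.94/5.16) × φ(z_q)/(1−q) = 3.86 × φ(z_q)/(1−q).
- 4 of 40 lost in each arm: 3.86 × 0.195 = 0.75 within each arm.
- 2 v 6: 3.86 × (0.274 − 0.109) = 0.64 in A v B.
- 0 v 8: 3.86 × 0.350 = 1.35 in A v B.

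Simulation with finite arms agrees and adds the model's result (bias in points, no true difference):

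| Loss driven by | A v B, completers (2 v 6 / 0 v 8) | A v B, model | Within arm at 4 v 4, completers | Within arm, model |
|---|---|---|---|---|
| Seen month-1 change | 0.63 / 1.34 | −0.01 / 0.02 | 0.71 | −0.02 |
| Unseen month-3 change | 0.61 / 1.32 | 0.24 / 0.53 | 0.73 | 0.31 |
| Change, lost before month 1 | 0.63 / 1.34 | 0.58 / 1.26 | 0.73 | 0.69 |

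If leavers are drawn at random from the less-improved half, completer bias is roughly half as large: 0.37 to 0.38 at 2 v 6, 0.73 to 0.76 at 0 v 8, and 0.32 to 0.35 within arm.

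**The case against.** The strongest reply is that 10.5 is under-specified rather than wrong: a likelihood fit could also be called a repeated-measures analysis, and baseline is probably already one level of the time factor. That stands in part. A reader might infer that the plan prescribes a complete-case analysis; it does not. But the usual meaning of the named method leads there, and nothing in the plan prevents it.

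A reader might also set the ANOVA group-by-time test against the model's averaged contrast and claim gains of 0.78 to 0.87 on full data and 0.63 to 0.85 with 10% missed. Those pairs change the contrast and the model together. Step 2 gives the fair comparison, and on full data the gain is small.

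The bias scenarios are stylised. No section suggests unequal loss between two active schedules, and 0 v 8 is an extreme. Gentler score-dependent drop-out gave a completer bias of 0.1 to 0.6 points, and up to 0.7 at heavier loss. All the figures lie below the 2-point threshold for mild disease in 2.1. This limits the severity but does not supply the missing rule.

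Section 5.3 has anyone who is "withdrawn from the study or has completed all visits should be de-enrolled from the research database within 48 hours". It is tempting to read this as loss of later scores. It applies equally to men who have finished, so it may be only a database status; it is weak evidence that gaps are likely.

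Finally, 10.5 also names SEP2 co-primary endpoints, and 7.3 and 7.4 contradict each other on PDE5i use after treatment. Both must be reconciled, and no model for the IIEF-EF does that.

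**Conclusion.** The point holds and should be acted on. The stated method for the primary score, as classically run, does not deliver the intention-to-treat analysis of 5.3, and a better standard method is available. The certain defect is the absence of a missed-visit rule, fitting method and baseline covariate. Its size depends on assumptions: pilot SDs, correlations of 0.5 and 0.7, a 3-point difference, and 5% to 10% of visits missed.

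Under these, the loss is 11 to 22 of 80 men and, at 10% missed, about 14 points of power for the averaged contrast (0.71 v 0.85) or 7 for the test across visits (0.63 v 0.70). With selective loss after month 1, completers are off by about 0.7 points within arm, and by about 0.6 in A v B at 2 v 6.

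It would go too far to say that the mixed model cures the problem. Some power is still lost (0.87 to 0.85 at 10% missed), it removes bias only as far as loss depends on recorded scores, and it does almost nothing for men lost before month 1.

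**What to change.** In 10.5, replace repeated-measures ANOVA for the IIEF-EF with a likelihood-based mixed model using all available scores of every randomised man in his assigned arm, with arm, visit, arm-by-visit and unstructured covariance. Enter the post-washout score of 7.3 as a covariate, or as a first outcome with a common mean in both arms. The second form keeps men with a baseline only and also yields the within-arm change of 2.2 and 3.1.

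- Keep the arm comparison over visits as the test of trends, and report A-B differences at months 1, 3 and 6. Whether an averaged contrast becomes the main test is for the sponsor to decide. On full data it has power 0.87 for a constant 3-point difference but 0.34 if the difference fades (3, 1.5, 0 points), where the joint test has 0.80.
- State the missing-at-random assumption, and report by arm the randomised men with no baseline or no follow-up score.
- Add one delta-adjusted imputation that includes men lost before month 1. A penalty of D points on their scores moves A v B by (6/40 − 2/40) × D = 0.10 D at 2 v 6, and by (8/40) × D = 0.20 D at 0 v 8.
- Reconcile 7.3 with the study calendar so that the baseline score is fixed, and 7.3 with 10.6 on when randomisation happens.

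The cost is SAP wording and one sensitivity analysis, with no added patients. No visit is added either, provided that the post-washout questionnaire of 7.3 is confirmed. The statistical price is a somewhat weaker joint test if no scores are missing (0.72 v 0.78).

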7.4 Treatment Procedures

The treatment session lasts approximately 20 minutes and may be performed in an office environment. Treatment is applied in the physician's office. For session and treatment details (see below)

During the treatment, the same total number of shocks will be delivered according to the two treatment schedules as follows:

Group A:

5 daily sessions within a week (MTWThF), in which 720 shocks of treatment energy will be applied in every session to each treated region (left and right corpora cavernosa and crura).

Group B:

Three sessions per week (MWF) for 2 consecutive weeks, in which 600 shocks of treatment energy will be applied in every session to each treated region (left and right corpora cavernosa and crura)

Following the last treatment session, each patient will resume his baseline consumption of PDE5i, in terms of type and dose of drug, for the remainder of study duration.

7.5 Follow-Up Procedures and Evaluations:

Follow-up visits will be conducted at month 1, month 3 and month 6 after the last treatment session and shall include:

Measuring IIEF-EF, GAQ, SEP, and EHS scores of patients at the clinic at every follow-up visit

Reporting and recording adverse events at every follow-up visit.

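### Fisher's exact test for SEP, GAQ and success rates runs at about 3% instead of 5% per comparison at 40 vs 40; Boschloo's test would recover modest power, and a test across visits is an optional supplement

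*Combined protocol and SAP*

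**What the plan says.** Section 10.5 says "GAQ, SEP and success rates will be analyzed and compared between the groups according to" Fisher's exact test. The sentence speaks of each endpoint, not of each visit. Two other places point to visit-by-visit testing. Section 10.2 lists the endpoint as "SEP 2 & 3 at follow-ups", with GAQ listed the same way. Section 7.5 says "Follow-up visits will be conducted at month 1, month 3 and month 6 after the last treatment session" and provides for "Measuring IIEF-EF, GAQ, SEP, and EHS scores of patients at the clinic at every follow-up visit".

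For level and size, 10.5 says "The statistical significance will be set at" P < 0.05, and 10.6 says "80 patients will be randomized 1:1 to treatment groups with 40 patients each". No multiplicity rule is given for these A vs B tests.

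The scored outcomes are handled differently: "IIEF-EF and EHS scores will be analyzed using ANOVA with repeated measures throughout the study". No repeated-measures analysis is named for the binary outcomes, and no reason is given for the difference.

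**The concern.** Fisher's test conditions on the total number of responders. At 40 per arm its P-values are so discrete that the rejection rate under no difference falls well short of the nominal 5%. The unused error is lost power.

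Each man also answers the SEP and GAQ items at three visits, yet nothing in 10.5 brings those answers together.

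At stake is the chance of seeing a real difference between two schedules on the named secondary endpoints. Section 7.1 makes evaluation of the two schedules the design aim. The only power figure in the plan concerns a comparison with placebo, so none is stated for A vs B.

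**Working it through.** **Inputs from the documents.** 40 vs 40 (10.6); nominal 0.05 (10.5); visits at months 1, 3 and 6 (7.5); one Yes/No answer per item (Appendices II and III).

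**Assumed inputs.** Response rates in A and B, and the within-man correlation over visits. The documents give neither, so ranges are shown.

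**1. The plan's own figure.** Figure 1 gives 0.852 for 5% vs 35% with 40 per group at alpha 0.025. The Walters approximation is

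power = Φ( √(2n) · [arcsin√(p₂ − 1/(2n)) − arcsin√(p₁ + 1/(2n))] − z₁₋α/₂ ).

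With n = 40, the bracket is arcsin√0.3375 − arcsin√0.0625 = 0.6199 − 0.2527 = 0.3672. Then √80 × 0.3672 = 3.284, and 3.284 − 2.241 = 1.043, so power is 0.852. The 37 and 45 per group rows (0.813 and 0.900) also reproduce. Exact enumeration of Fisher's test at 40 per group gives 0.850. Figure 1 therefore already allows for Fisher's conservatism.

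**2. Actual size of Fisher's test.** Let b(·; 40, π) be the binomial probability. Size is the sum of b(x; 40, π)·b(y; 40, π) over all cells (x, y) of the 41 × 41 table whose two-sided Fisher P is at most 0.05.

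| Common rate π | 5% | 10% | 20% | 35% | 40% | 50% |
|---|---|---|---|---|---|---|
| Actual size | 0.4% | 1.7% | 2.8% | 2.8% | 3.0% | 3.3% (maximum) |

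The values are symmetric above 50%. With 36 per arm (10% lost) the maximum is 2.8%.

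**3. Boschloo's test at one visit.** It uses the Fisher P-value as its statistic and sets the cut-off so that the largest size over π stays at or below 5%. At 40 vs 40 the cut-off is a Fisher P of 0.0707, with a maximum size of 4.77%. Every table that Fisher rejects is also rejected by Boschloo.

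| Assumed rates | Fisher | Boschloo | Gain |
|---|---|---|---|
| 35% vs 50% | 0.21 | 0.26 | 5 points |
| 35% vs 60% | 0.550 | 0.586 | 4 points |
| 35% vs 65% | 0.724 | 0.749 | 2.5 points |
| 50% vs 75% | 0.559 | 0.638 | 8 points |

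With 36 per arm the gain is about 9 points (35% vs 65%: 0.631 to 0.718; 50% vs 75%: 0.496 to 0.586). Mid-p and Pearson chi-square gain more in places, but at 40 vs 40 their size reaches 5.7% and 5.9%.

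**4. Combining the three visits.** Simulation with latent-normal correlation 0.5 / 0.7 / 0.85. The combined test compares each man's average of three answers, close to an independence GEE. Under no difference its size is 4.9% to 5.0%. Three unadjusted Fisher tests give at least one false positive in 6.6% to 7.9% of runs.

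Power with a constant effect:

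| Assumed rates | Combined test | Fisher at 0.05/3 per visit | Difference |
|---|---|---|---|
| 35% vs 65% | 0.95 / 0.92 / 0.87 | 0.84 / 0.80 / 0.76 | 11 to 12 points |
| 50% vs 75% | 0.88 / 0.82 / 0.76 | 0.67 / 0.63 / 0.58 | 18 to 21 points |

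Power when the effect is not constant (35% in the other arm throughout):

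| Rates at months 1, 3, 6 | Combined test | Comparison |
|---|---|---|
| 65%, 55%, 45% | 0.69 to 0.56 | 0.62 to 0.58 (Fisher at 0.05/3 per visit) |
| 65%, 50%, 35% | 0.46 to 0.37 | about 0.72 (Fisher at month 1 alone) |
| 65%, 35%, 35% | 0.24 to 0.20 | about 0.72 (Fisher at month 1 alone) |

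**The case against.** Fisher's test is valid: it guarantees that each comparison stays at or below 5%, which chi-square and mid-p do not at this size. Visit-specific tests also answer a question of their own, because time course matters in a study with follow-up at 1, 3 and 6 months. Both points stand. They rule out saying that the plan gives up power for nothing, or that it throws answers away: on the natural reading every visit's answers are tested, but never combined.

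A reader might infer that a combined test lifts power from 0.72 to between 0.87 and 0.95. That sets three visits against one. On the same assumptions (35% vs 65%), the planned three unadjusted tests give at least one significant visit in 0.89 to 0.94 of runs. What differs is the error rate. The fair comparison is with visit tests held to 5% overall, as in step 4, and that advantage depends on a constant effect.

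A reader might also infer that the plan as a whole uses only 3% of its 5%. That is true of one test only; over three unadjusted visits an item exceeds 5%.

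Finally, both arms are active and receive the same total number of shocks according to 7.4, so gaps of 25 to 30 points have no basis in the documents. At 35% vs 50% power stays low with either test. This stands, and limits what any change of test can achieve.

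**Conclusion.** The point holds as an optional efficiency improvement on secondary endpoints. At 40 vs 40 each Fisher comparison has an actual size of about 3% at rates between 20% and 80%, and less at the extremes. Boschloo's test keeps the 5% guarantee and adds 2.5 to 8 points of power at one visit under the assumed rates.

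Replacing the visit tests by a combined test is not supported. It is a trade-off that turns on whether the effect persists, and the documents do not say. Nor is Figure 1 wrong on this account: it was computed for Fisher's test, for a 5% vs 35% comparison with placebo at 0.025 ("Each of these tests will be conducted with a 0.025 alpha error level to allow for a 0.05 experiment wide type I error rate"), not for A vs B.

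The conclusion rests on the per-visit reading of 10.5, which is inferred, and on assumed rates and correlations. The size figures need no assumption about the treatment effect.

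**What to change.** In 10.5:

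- State that SEP2, SEP3, GAQ and success rates are compared at months 1, 3 and 6, if that is what is meant.
- Replace Fisher's test by Boschloo's unconditional exact test for single-visit A vs B comparisons, and report each risk difference with a 95% CI.
- State the multiplicity rule over visits. Boschloo's test uses more of the error at each visit, so if it is left unadjusted the ceiling for one item over three visits rises from 3 × 3.3% = 9.9% to 3 × 4.77% = 14.3%.
- Optionally, where a visit-averaged effect is of interest, add one GEE logistic test of arm over the three visits, with a small-sample correction, for SEP2, SEP3 and GAQ-Q1. Present it beside the visit results, and say how missed visits are handled.
- Leave GAQ-Q2 out of the combined analysis, or count No on Q1 as No on Q2, because Appendix III asks Q2 only of men who answer Yes to Q1.

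The cost is SAP wording and a few lines of code, with no new data or patients. The drawbacks are slightly less familiar software and a modest gain.

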6. PATIENT SELECTION/ELIGIBILITY CRITERIA

6.1 Inclusion (Eligibility) Criteria

- The patient must be able willing and able to provide informed consent.
- The patient is a male between ≥ 30 and ≤ 80 years of age.
- The patient has ED of Vasculogenic origin determined by penile duplex ultrasound.
- The patient is PDE5i responsive, meaning he is able to achieve and maintain an erection under the effect of the maximal dosage of PDE5i.
- The patient has been in a stable heterosexual relationship for over 3 months prior to enrollment.
- A minimum of 2 sexual attempts per month for at least one month prior to enrollment – as documented by the Sexual Health Questionnaire (SHIM).
- The patient is suffering from erectile dysfunction lasting for over 6 months and not more than 5 years as per history provided by patient.
- IIEF-EF score between 11 and 25.
- Testosterone level 300-1000 ng/dL within 1 month prior to enrollment.
- A1C level $\leq 7\%$ within 1 month prior to enrollment.
- Patients have at least a natural tumescence during sexual stimulation (EHS score ≥ 1).

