7. STUDY DESIGN, CLINICAL, RADIOLOGICAL, LABORATORY AND SURGICAL EVALUATIONS

7.1 Study Design

This is a prospective, randomized, clinical study aimed to evaluate the safety and efficacy of the two treatment schedules on symptomatic ED patients. The patients are randomized in a 1:1 ratio into two active treatment groups. (Refer section 18)

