7.2 Screening Evaluations and Procedures

The first visit of the patients will be for screening and medical evaluation. Patient's medical co-medication history will be collected and documented and a physical examination will be performed.

Previous month's blood test results will be reviewed including a general chemistry panel, a lipid profile, A1C and Testosterone levels during chart review.

Patients will sign an informed consent and will answer the IIEF-EF questionnaire to see if they fit the criteria for enrollment. In case they meet all inclusion criteria (and do not meet any exclusion criteria), they will be recruited to the study.

[figure not shown]
Patients who have been using PDE5-i in the last 4 weeks will report on their medicine type and dosage, and this data will be recorded in their files (reported prior to consent and gathered from chart review).

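### Section 10.5 sizes the trial on men who all fail SEP2, but eligibility does not select on SEP2 and no use of the baseline answer is stated, so an arm's pass rate may not be a conversion rate

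*Combined protocol and SAP*

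**What the plan says.** The sample-size text in 10.5 starts from this population: "A sample of 80 men with failing scores on the IIEF SEP2 question will be randomized 1:1 into one of two arms". It assumes that 0-5% pass SEP2 after placebo and at least 35% after either active treatment. With 40 per group and alpha 0.025 per test, it states at least 85% power. It calls the SEP2 pass percentages co-primary, whereas 3.1 and 10.1 make IIEF-EF primary and 3.2 and 10.2 list SEP among the secondary measures. The term failing is not defined; I read it as No to SEP-Q2 in Appendix II.

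The eligibility lists in 6.1 and 6.2 do not mention SEP2. They require "IIEF-EF score between 11 and 25" and an EHS of at least 1, with no upper limit on EHS. The alternate hypothesis in section 2 expects mild as well as moderate disease: "increase in the IIEF-EF score from baseline for mild erectile dysfunction, and >5 points for moderate erectile dysfunction". At screening (7.2), men "will answer the IIEF-EF questionnaire to see if they fit the criteria for enrollment".

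Section 7.3 collects SEP after the washout and before the first session. Section 10.2 lists SEP 2 and 3 at follow-ups, and 10.5 compares SEP between groups with Fisher's exact test. Neither gives the baseline answer a role.

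**The concern.** If every man fails SEP2 at entry, the share passing at follow-up is the share who converted, and it can be set beside the 35% in 10.5. If some men already pass, the follow-up rate mixes conversions with men who simply continue to pass.

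The trial has no sham or placebo arm (7.1: "The patients are randomized in a 1:1 ratio into two active treatment groups"), so readers are likely to judge each schedule by its own SEP2 rate. That rate could look better than the planning assumption without any added benefit. A real difference in conversion between schedules would also appear smaller than it is. The sample-size paragraph would describe men whom the eligibility criteria do not select.

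**Working it through.** **1. The plan's own figure.** Inputs from 10.5: 5% versus 35%, alpha 0.025 (two-sided reproduces the table), n = 40 per group, Walters approximation.

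Power = Φ(√(2n)·[asin√(p2 − 1/(2n)) − asin√(p1 + 1/(2n))] − z)
= Φ(√80·[asin√0.3375 − asin√0.0625] − 2.241) = 0.8515, against 0.852 stated. At n = 37 and n = 45 the formula gives 0.8134 and 0.9004, against 0.813 and 0.900. The arithmetic is sound for active versus placebo in men who all fail SEP2.

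**2. Can a man who passes SEP2 be eligible?** Inputs: the item scores in Appendix I. A man with no penetration in the past 4 weeks, answering consistently, scores at most 1 on each of items 3, 4 and 5. His highest total is 5 + 5 + 1 + 1 + 1 + 5 = 18. The eligible range 11-25 has 15 values, and the 7 from 19 to 25 imply some penetration, hence a SEP2 Yes over the same period.

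**3. What follow-up status then shows.** Assumed, not in the documents: q, the share passing at baseline (0-50%), and r, the share of those who still pass at follow-up (100%, with 90% as a check). Conversion is set at the plan's 35%.

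Arm pass rate = q·r + (1 − q)·0.35

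| q | r = 100% | r = 90% |
|---|---|---|
| 0 | 35.0% | 35.0% |
| 10% | 41.5% | 40.5% |
| 25% | 51.3% | 48.8% |
| 50% | 67.5% | 62.5% |

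**4. Dilution of A versus B.** With equal r in both arms, the difference in pass rates is (1 − q) times the difference in conversion. For conversion of 35% versus 65%, the 30 points become 27, 22.5 and 15 at q = 10%, 25% and 50%. Exact Fisher power with 40 per arm, two-sided 0.05 and r = 100% is 0.724, 0.623, 0.463 and 0.262 at q = 0, 10%, 25% and 50%. The type I error at equal 35% conversion stays between 0.028 and 0.033.

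**5. What stratifying by baseline SEP2 gains.** For 35% versus 50% conversion, the Cochran-Mantel-Haenszel test against the unstratified chi-square test has power 0.250 versus 0.245 at q = 10%, and 0.216 versus 0.183 at q = 25%. With r = 90% there is no gain at q = 10%, and 0.198 versus 0.185 at q = 25%.

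**6. Precision on the conversion scale.** The 95% half-width for A minus B among baseline failers, with m per arm and 35% conversion in both, is 1.96·√(2·0.35·0.65/m):
- m = 40: 20.9 points
- m = 36: 22.0 points
- m = 30: 24.1 points
- m = 20: 29.6 points

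With no losses, these m correspond to q = 0, 10%, 25% and 50% of 40 men.

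**The case against.** **Screening scores do not settle the baseline.** The IIEF-EF used for entry precedes the washout. Section 6.1 requires that "The patient is PDE5i responsive, meaning he is able to achieve and maintain an erection" at maximal PDE5i dosage, and 7.2 expects some recent users: "Patients who have been using PDE5-i in the last 4 weeks will report on their medicine type and dosage". Some totals of 19-25 may reflect function on drug, and those men may fail SEP2 once washed out. This stands. A reader might infer from 7 of 15 eligible totals that nearly half the sample passes at baseline. The documents do not support that: 7 of 15 counts score values, not men, and q is unknown.

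**The whole paragraph describes another design.** The 85% is for active against placebo, and the trial has no placebo arm. This also stands, and it limits what can be claimed. On 10.5's own inputs, exact power falls from 0.850 to 0.602 if 10% already pass and keep passing, and a reader might conclude that the trial loses that power. It does not, because that comparison will not be made; the figure shows only how sensitive the calculation is to its premise. Rewriting the paragraph for two active schedules would remove the population sentence, but the SEP2 analysis would still give the baseline answer no role.

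**The baseline may be intended.** Sections 3.2 and 10.2 speak of improvement, and the success rates in 10.5 are undefined. A change from baseline could be meant, but no rule says so.

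**Bias.** A reader might infer that the A-versus-B test is biased or its type I error inflated. Neither follows, since 1:1 randomization balances baseline passers on average.

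**Stratifying does not undo the dilution.** A stratified difference in all men still carries the factor 1 − q. Its half-width at q = 25% and r = 100% is 18.1 points, which looks better than 20.9 only because the target has shrunk: 18.1/0.75 = 24.1 on the conversion scale. This is why precision belongs on that scale.

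**Conclusion.** The mismatch is certain from the text: 10.5 assumes a sample made up only of SEP2 failers, 6.1 and 6.2 do not select one, and no use of the baseline answer is stated. Its size is conditional. If q is above zero and most baseline passers keep passing, each arm's pass rate overstates conversion (41.5% to 67.5% instead of 35% over q of 10-50% with r = 100%), cannot be read against the 35% in 10.5, and shows a difference in conversion diluted by 1 − q. If q is zero, none of this arises.

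The A-versus-B comparison remains unbiased and the IIEF-EF analysis is untouched. How much the point weighs depends on whether SEP2 is co-primary (10.5) or secondary (3.2, 10.2); those passages must be reconciled. The figures assume complete follow-up. At the 10% loss that 10.5 itself considers, 40 per arm becomes 36, and the half-width with q = 0 rises from 20.9 to 22.0 points.

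Sections 7.3 and 7.4 contradict each other on PDE5i during follow-up. That also affects SEP2 and must be reconciled, but it is a separate matter, and the 35% conversion model above does not represent it.

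**What to change.** 1. Rewrite the 10.5 sentence so that the sample-size text describes the men enrolled under 6.1, defines failing, and no longer presents 35% as the pass rate of a sample made up only of SEP2 failers. Do not carry the 85% over to A versus B; it applies only to active versus placebo in men who all fail.
2. Keep all randomized men in the A-versus-B SEP2 test, in line with 5.3, stratified by the post-washout SEP2 answer from 7.3, with men lacking that answer as their own stratum. Report each arm's pass rate by baseline SEP2. Report No-to-Yes conversion among baseline failers with its 95% CI as the estimate that is not diluted. Align the section 17 calendar with 7.3: it shows the questionnaires at screening and follow-up but not at the pre-treatment visit.
3. State precision on the conversion scale at 35% conversion: about 21 points either side with 40 failers per arm, 22 with 36, 24 with 30 and 30 with 20, noting that dropout widens it.

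The cost is a rewritten paragraph, one stratified analysis, one table and a calendar correction. No new visit, eligibility change or data item is needed if SEP is collected as 7.3 states. There are downsides: q is unknown in advance, so precision has to be given as a range; stratifying gains almost no power if q is small; the failers-only estimate rests on fewer men; and the stated precision will look less favourable than 85% power.
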